### 12.4 APPENDIX D: CONSENSUS CONFERENCE CLINICAL GRADING OF ACUTE GVHD(96)

### **Clinical Staging**

Stage	Skin	Liver: Total Bilirubin	Intestinal Tract: Diarrhea
0	No rash	<2.0 mg/dL	< 500 ml/day
1	<25% of skin surface	2.0-3.0	500-1000 ml/day
2	25-50%	3.1-6.0	1001-1500 ml/day
3	Erythroderma	6.1-15.0	>1500 ml/day
4	Erythroderma with bullae and desquamation	>15.0	Severe abdominal pain with or without ileus

### **Clinical Grading**

Grade	Grade Skin*		GI
I	1-2	0	0
П	3	1	1
III	-	2-3	2-4
IV	4	4	-

\*Each column identifies minimum stage for organ grade.

### 12.5 APPENDIX E: GRADING OF CHRONIC GVHD(97)

	SCORE 0	SCORE 1	SCORE 2	SCORE 3
PERFORMANCE SCORE: KPS ECOG LPS	Asymptomatic and fully active (ECOG 0; KPS or LPS 100%)	Symptomatic, fully ambulatory, restricted only in physically strenuous activity (ECOG 1, KPS or LPS 80-90%)	Symptomatic, ambulatory, capable of self-care, >50% of waking hours of of bed (ECOG 2, KPS or LPS 60- 70%)	>50% of waking
SKIN† SCORE % BSA  GVHD features to be scored by BSA: Check all that apply: Maculopapular rash/eryth Lichen planus-like feature Sclerotic features Papulosquamous lesions of ichthyosis	involved ema es	1-18% BSA	19-50% BSA	>50% BSA
Keratosis pilaris-like GVI SKIN FEATURES SCORE:	No sclerotic features		Superficial sclerotic features "not hidebound" (able to pinch)	Check all that apply:  Deep sclerotic features  "Hidebound"  (unable to pinch) Impaired mobility Ulceration
Other skin GVHD features ( Check all that apply: Hyperpigmentation Hypopigmentation Poikiloderma Severe or generalized pru Hair involvement Nail involvement Abnormality present but e	ıritus	on-GVHD documented	cause (specify):	
MOUTH Lichen planus-like features present: Yes No Abnormality present but e	No symptoms explained entirely by no	Mild symptoms with disease signs but not limiting oral intake significantly on-GVHD documented	disease signs with partial limitation of oral intake	Severe symptoms with lisease signs on xamination with major imitation of oral intake

Version 10 29 March 2023

	SCORE 0	SCORE 1	SCORE 2	SCORE 3
EYES  Keratoconjunctivitis sicca (KCS) confirmed by ophthalmologist: Yes No Not examined	No symptoms	Mild dry eye symptoms not affecting ADL (requirement of lubricant eye drops ≤ 3 x per day)	Moderate dry eye symptoms partially affecting ADL (requiring lubricant eye drops > 3 x per day or punctal plugs), WITHOUT new vision impairment due to KCS	Severe dry eye symptoms significantly affecting ADL (special eyeware to relieve pain) OR unable to work because of ocular symptoms OR loss of vision due to KCS
Abnormality present bu	t explained entirely b	y non-GVHD documented	l cause (specify):	
GI Tract  Check all that apply:  Esophageal web/ proximal stricture or ring Dysphagia Anorexia Nausea Vomiting Diarrhea Weight loss ≥5%* Failure to thrive	No symptoms	Symptoms without significant weight loss* (<5%)	Symptoms associated with mild to moderate weight loss* (5-15%) OR moderate diarrhea without significant interference with daily living	Symptoms associated with significant weight loss* >15%, requires nutritional supplement for most calorie needs OR esophageal dilation OR severe diarrhea with significant interference with daily living
Abnormality present bu	t explained entirely b	y non-GVHD documented	cause (specify):	
LIVER  Abnormality present bu	Normal total bilirubin and ALT or AP < 3 x ULN t explained entirely b	Normal total bilirubin with ALT ≥3 to 5 x ULN or AP ≥ 3 x ULN y non-GVHD documented	Elevated total bilirubin but ≤3 mg/dL or ALT > 5 ULN d cause (specify):	Elevated total bilirubin > 3 mg/dL
Lungs**		,	(0)	
Symptom score:	No symptoms	Mild symptoms (shortness of breath after climbing one flight of steps)	Moderate symptoms (shortness of breath after walking on flat ground)	Severe symptoms (shortness of breath at rest; requiring $0_2$ )
Lung score: % FEV1  Pulmonary function tests	FEV1≥80%	FEV1 60-79%	FEV1 40-59%	FEV1 ≤39%
Not performed  Abnormality present bu	t explained entirely b	y non-GVHD documented	l cause (specify):	

S	CORE 0	SCORE 1	SCORE 2	SCORE 3	
P-ROM score (see below) Shoulder (1-7): Elbow (1-7): Wrist/finger (1-7): Ankle (1-4):  Abnormality present but	No symptoms	Mild tightness of arms or legs, normal or mild decreased range of motion (ROM)  AND not affecting ADL	Tightness of arms or legs OR joint contractures, erythema thought due to fasciitis, moderate decrease ROM AND mild to moderate limitation of ADL tented cause (specify):	Contractures WITH significant decrease of ROM AND significant limitation of ADL (unable to tie shoes, button shirts, dress self etc.)	
GENITAL TRACT (See Supplemental figure ‡ ) Not examined Currently sexually active Yes No		Mild signs ‡ and females with or without discomfort on exam	Moderate signs ‡ and may have symptoms with discomfort on exam	Severe signs ‡ with or without symptoms	
Abnormality present but					
Other indicators, clinical score to severity (0-3) bas					
Ascites (serositis)	Myasi	thenia Gravis			
Pericardial Effusion	Peripl	neral Neuropathy	Eosinophilia > 500/µl		
Pleural Effusion(s)	Polyn	nyositis	Platelets <100,000/µl		
Nephrotic syndrome_	Weight loss>5%* without GI symptoms Others (specify):				
Overall GVHD Severity (Opinion of the evaluator)	□ No GV	/HD  Mild	☐ Moderate	☐ Severe	
Photographic Range of M	lotion (P-ROM)	)	*		
	Shoulder	7 T T T	6 7 (Normal)		
	Elbow &	2 3 4 5	6 7(Normal)		
	Wrist/finger	2 3 4 5	6 7 (Normal)		
	1 (Wo	2 3 4(Normal)			

- † Skin scoring should use both percentage of BSA involved by disease signs and the cutaneous features scales. When a discrepancy exists between the percentage of total body surface (BSA) score and the skin feature score, OR if superficial sclerotic features are present (Score 2), but there is impaired mobility or ulceration (Score 3), the higher level should be used for the final skin scoring.
- \* Weight loss within 3 months.
- \*\*Lung scoring should be performed using both the symptoms and FEV1 scores whenever possible. FEV1 should be used in the final lung scoring where there is discrepancy between symptoms and FEV1 scores. Abbreviations: ECOG (Eastern Cooperative Oncology Group), KPS (Karnofsky Performance Status), LPS (Lansky

Performance Status); BSA (body surface area); ADL (activities of daily living); LFTs (liver function tests); AP (alkaline phosphatase); ALT (alanine aminotransferase); ULN (normal upper limit).

‡ To be completed by specialist or trained medical providers (see Supplemental Figure).

#### 12.6 APPENDIX F: CRITERIA FOR DOSE ESCALATION

Dose escalation will occur if 0 out of the first 3 patients experience DLTs. Rules for dose escalation are as follows:

**0/3 DLTs:** Escalate the dose (dose levels 1-2), or halt dose escalation (dose level 3).

1/3 DLTs: Study an additional 3 patients. If an additional patient experiences a DLT, halt dose escalation. If no other patient experiences DLT (that is if 1/6 patients on dose level experiences DLT), escalate the dose (dose levels 1-2) or halt dose escalation (dose level 3).

2/3 DLTs: Halt dose escalation.

The decision to escalate the dose of donor peripheral blood cells and to enroll patients to the higher dose level may not be made until one of the following has occurred:

- 1. The first 3 patients have been fully evaluated for DLTs and none has experienced a DLT.
- 2. Six patients have been fully evaluated and only 1 has experienced a DLT.

The DLT observation window continues until the first of the following:

- 1. ANC > 500/microL AND confirmation the DLI has been rejected (either bone marrow donor chimerism <5% or donor blood CD3+ chimerism <5%)
- 2. Within 56 days following NE-DLI

If neither of these conditions has been met, patients will continue to be accrued to the current dose level. In the event that 0/3 patients experience DLT, accrual to the next higher dose level may proceed even if additional patients have been treated at the lower dose level and are not yet evaluable. However, if any of those patients experience DLT, accrual to the higher dose level will be suspended until a total of 6 patients have been treated and evaluated at the lower dose level. Further accrual to the higher dose level will not resume until the DLT incidence in the lower dose level is documented to be no greater than 1/6 patients. Accrual to the higher dose level will be stopped if the incidence of DLTs in the previous level exceeds 33% (for instance, if none of the first 3 patients experiences DLT, but the next 2, who were accrued during the observation period for the first 3 patients, do).

DLTs are defined as any of the following that is at least possibly attributable to the investigational treatment:

- 1. Grade 2-4 infusion toxicity
- 2. Grade 4 organ toxicity (as defined by NCI CTCAE v 5.0), not preexisting, not due to the primary malignancy, and not due to chemotherapy or infection
- 3. Grade 3 organ toxicity that does not resolve within 14 days and which is not preexisting, not due to the primary malignancy, and not due to chemotherapy or infection
- 4. Grade 2-4 acute GvHD
- Delayed neutrophil recovery: ANC>500/μl does not occur within 56 days AND measurable donor chimerism is >5%
- 6. Grade 3-4 CRS; see Appendix for grading scheme)
- 7. Any Grade 5 reaction other than progressive disease.

If 2 or more of the first 6 patients on any dose level experience DLTs, accrual to the trial will be suspended and the sponsor of the IDE (the PI) will initiate a formal consultation with the FDA in order to determine whether the

CD8-depleted non-engrafting HLA antigen-mismatched unrelated donor lymphocyte infusion... Protocol <20042> Version 10 29 March 2023

observed toxicities are or are not attributable to the device. Subsequent accrual to the trial may resume only with permission from the FDA. Any questions or concerns as to the relationship of grade > 3 toxicities to use of the investigational device will be discussed with the appropriate FDA Clinical Review Staff.

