# **Study Population:**

**Eligible patients** will have a MDS with progression or lack of response after at least 4 cycles of a HMA or sAML. HMA failure will be defined by the IWG criteria or intolerance to the drug (1)

**Number of Patients:** Expected 15 in the phase Ib cohort and 10 in the phase II cohort. 28 patients maximum. (The number of patients in the phase I cohort can be as high as 18 (6 patients for each dose level).)

Phase: Phase 1b/2

Version 10 29 March 2023

Description of Sites/Facilities Enrolling Participants: H. Lee Moffitt Cancer Center – Single Site

Description of Study Intervention:

Eligible subjects will receive intensive cytotoxic induction chemotherapy with any standard of care cytarabine-based regimen. Twenty-four to 36 hours after chemotherapy cessation, subjects will receive NE-DLI infusion at a dose determined by their dose cohort in phase 1 or the recommended phase 2 dose in phase 2. Subjects will remain hospitalized to receive supportive care during the period of aplasia, and after being discharged from the hospital they will undergo weekly study visits until day 56 from DLI infusion for toxicity

assessments

Study Duration: 3-4 years

Participant Duration: 12 months

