# 4.3 JUSTIFICATION FOR DOSE

For the dose-escalation portion, a minimum of 2 subjects and a maximum of 18 subjects will be enrolled. There will be 3 dose levels in the dose-escalation portion. MTD is defined as the highest dose level with the probability of DLT less than 33% (DLT events are defined in Section 6). The DLT observation window will be within 56 days following NE-DLI. If none of 3 patients experience a DLT, we will escalate to the next dose level. If one of the 3 patients experiences a DLT, we will enroll 3 additional patients and treat at the same dose level. In this case, if none of these additional 3 patients experiences a DLT, we will escalate to the dosage to next level. If 2 or more patients

among 6 enrolled patients experience a DLT, or 2 or more patients in the 3 patient cohort experience DLT, the dosage level exceeds the MTD and the previous dose level will be declared as the MTD. If the first dose level exceeds the MTD, the study will be suspended. If no subjects experience a DLT at any dose level, the MTD will be level 3 ( $5 \times 10^7$  CD4+ T cells/kg).

The RP2D is defined as the dose level selected to be evaluated in the expansion cohort or future phase II studies and will be equivalent to the MTD determined in the phase 1b portion of the study. Once we determine the RP2D level, we will enroll 10 additional eligible patients and treat with the RP2D level. The goal for this expansion cohort is to evaluate the safety and tolerability for patients who will be treated with NE-DLI in the RP2D dose level, and to evaluate the preliminary efficacy estimate for the ORR. Including the dose-escalation portion in which 3 or 6 enrolled patients will have been treated at the RP2D level, a total of at least 13 patients will be treated at the RP2D level. Based on previous data, (18) the complete response rate using microtransplantation was in the range of 36%-52% for MDS or AML from antecedent MDS patients. Hence, for the phase 2 portion, an ORR of 45% is considered clinically meaningful. With a sample size of 13 patients, if our ORR is 45%, the 95% CI (exact binomial) will be (18-74%); if the ORR is 50%, the 95% CI will be (22-78%).

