# 4.4 END OF STUDY DEFINITION

The phase I portion of the study will continue until reaching the MTD to determine the RP2D. The phase II portion of the study will continue until an additional 10 patients are treated at the RP2D. The maximum total number of patients enrolled in this study will be 28 (6 per dose level plus 10 in the expansion cohort). We expect that the accrual rate will be one patient per every 5-6 weeks. With the DLI observation window (56 days after DLI), the dose-escalation portion may take up to a maximum of 2.5 - 3 years to complete and an additional 1.5 years for the expansion cohort.

A participant is considered to have completed the study if he or she has completed all phases of the study including the last visit or the last scheduled procedure shown in the SOA, Section 1.3.

The end of the study is defined as completion of the last visit or procedure shown in the SOA in the trial globally.

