In the case of a need to discontinue cytotoxic chemotherapy before infusion of cells, the patient will be taken off protocol because of toxicity. This will not be classified as a DLT in the phase 1 portion of the trial.

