# 9.4.2 ANALYSIS OF THE PRIMARY ENDPOINT(S)

For the dose escalation portion, a minimum of two subjects and a maximum of 18 subjects will be enrolled. There will be three dose levels in the dose escalation portion. MTD is defined as the highest dose level with the probability of DLT less than 33% (DLT events are defined in Section 6). The DLT observation window will be until confirmation that the donor cells have been rejected (ANC ≥ 500/microL AND confirmation of either bone marrow donor chimerism <5% or donor blood CD3+ chimerism <5%) OR within 56 days following NE-DLI, whichever occurs first. Per the traditional 3+3 schema, up to three patients may be enrolled concurrently and treated at the same dose level. The first three patients will be treated at dose level 1. For each dose level, if none of three patients experiences a DLT, we will escalate to the next dose level until reaching dose level 3. For each dose level, if one of the three patients experiences a DLT, we will enroll three additional patients and treat at the same dose level. In this case, if none of these additional three patients experiences a DLT, we will escalate the dosage to next level until reaching dose level 3. For each dose level, if two or more patients among six enrolled patients experience a DLT, or two or more patients in the three patient cohort experience DLT, the dosage level exceeds the MTD and the previous dose level will be declared as the MTD. If the first dose level exceeds the MTD, the study will be suspended. If no subjects experience a DLT at any dose level, the MTD will be level 3 (5 x 10^7 CD4+ T cells/kg). Similarly, if exactly one of six patients enrolled at dose level 3 experiences a DLT, then the MTD will be dose level 3. All patients in a dose level must be observed through the DLT window prior to enrolling patients at a higher dose level.

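### Appendix F sets no ceiling on accrual to a dose level under evaluation, which does not fit the stated maxima of 6 per level, 18 in escalation and 28 in total

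*Combined protocol and SAP*

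**What the plan says.** **The maxima.** The Synopsis (Study Population) states: "The number of patients in the phase I cohort can be as high as 18 (6 patients for each dose level". Section 4.4 states: "The maximum total number of patients enrolled in this study will be 28 (6 per dose level plus 10 in the expansion cohort", and Section 6.1.3 repeats this. Sections 4.3, 6.1.3 and 9.4.2 also give 18 as the escalation maximum. On the components, Section 4.3 says "There will be 3 dose levels in the dose-escalation portion" and "Once we determine the RP2D level, we will enroll 10 additional eligible patients and treat with the RP2D level".

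**The accrual rule.** Section 12.6 (Appendix F) allows escalation once the first three patients are fully evaluated with no DLT, or six are fully evaluated with one. It continues: "If neither of these conditions has been met, patients will continue to be accrued to the current dose level". No upper limit follows. The table in Section 6.1.4 asks for three or more further patients after 1/3, also without a limit. Section 9.4.2 says that "up to three patients may be enrolled concurrently and treated at the same dose level".

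**Pace and window.** Section 4.4 says: "We expect that the accrual rate will be one patient per every 5-6 weeks". The DLT window lasts at most 56 days after infusion. Section 9.4.2 and Appendix F close it earlier once neutrophils recover and donor chimerism is below 5%.

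**Opening the next level.** Section 9.4.2 requires every patient at a level to complete the window before a higher level enrols. Appendix F, after 0/3, lets the higher level start while further patients at the lower level cannot yet be evaluated.

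**Who counts.** Section 4.4 counts patients enrolled. Section 6.1.2.2 says: "In the case of a need to discontinue cytotoxic chemotherapy before infusion of cells, the patient will be taken off protocol", and adds that this is not a DLT.

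**The concern.** A maximum of 6 per level requires accrual to stop at the sixth patient while that patient is observed. Appendix F says the opposite: while the sixth patient is in the window, neither escalation condition is met, so accrual to that level goes on. The window can be longer than the gap between patients, so this can arise at the stated pace.

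Two things are at stake. First, staff who follow Appendix F can exceed the stated per-level limit and, in the worst case, the study total. If the total of 28 is enforced instead, the ten additional expansion patients may not fit. Second, the escalation rule is incomplete and inconsistent. Appendix F does not say how a seventh patient's outcome counts after 1/6, and Appendix F and Section 9.4.2 differ on when the next level may open.

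**Working it through.** **Inputs.** Three dose levels and ten expansion patients (Section 4.3); 6 per level and one patient every 5-6 weeks, that is every 35-42 days (Section 4.4); a DLT window of at most 56 days (Sections 4.3 and 9.4.2, Appendix F); escalation after 0/3 or 1/6 fully evaluated (Appendix F).

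**Step 1: the plan's own figure.** 3 x 6 = 18, and 18 + 10 = 28. This reproduces the stated maximum, provided accrual stops at the sixth patient of each level.

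**Step 2: Appendix F as written, even spacing, full windows.** Count days from the sixth patient's infusion.
- Seventh patient: day 35 to 42, inside the 56-day window.
- Eighth patient: day 70 to 84, after it closes.

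So one extra patient joins a level that needs six evaluated, giving 7. By the same reasoning a 0/3 level holds 4, which is within the cap. The limit of three concurrent patients in Section 9.4.2 does not prevent this, because at this spacing no more than two patients are in the window at once.

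**Step 3: totals.**
- All three levels need six: 7 + 7 + 7 = 21 in escalation, and 21 + 10 = 31.
- Extra level 3 patient counted among the ten: 31 - 1 = 30.
- Two levels need six and level 3 is 0/3: 7 + 7 + 4 = 18, so the escalation and study totals still hold although two levels exceed 6.

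**Step 4: early closure.** There is no excess if the window closes by day 35 (5-week spacing) or day 42 (6-week spacing). Section 8.4.3.3 says neutrophil recovery usually falls between days 21 and 42. The schedule of activities allows the chimerism sample as late as day 42 plus 3 days. Both outcomes are therefore possible.

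**Step 5: how likely.** Let p be the DLT probability at a level, which the documents do not give.
- Escalation after 1/3 then 0/3 has probability 3p(1-p)^5. For assumed p of 10%, 15%, 20%, 25% and 30% this is 0.177, 0.200, 0.197, 0.178 and 0.151. With full windows, a given level would exceed 6 by this route about 15-20% of the time.
- Under Appendix F a level can also reach 1/6 when the first three have no DLT but the fourth does: p(1-p)^5. The sum is 4p(1-p)^5, at most 0.268 (at p = 1/6).
- At level 3 the route to six starts with 1/3: 3p(1-p)^2, at most 0.444 (at p = 1/3).
- The path 7 + 7 + 7 therefore has probability at most 0.268 x 0.268 x 0.444 = 0.032, whatever the DLT rates. At a common rate between 10% and 30%, counting only the 1/3 route, it is 0.8% to 1.5%. Both figures leave out the back-fill to a lower level in Section 6.1.4.

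**Step 6: not a hard bound.** If arrivals cluster so that two patients enter during the sixth patient's window, the count is 3 x 8 + 10 = 34. Appendix F's own example has two patients entering during a window, though there they follow the first three.

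**Step 7: if 28 is enforced.** After 21 in escalation, 28 - 21 = 7 places remain for expansion instead of 10.

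**The case against.** The best defence is that Appendix F should be read together with the caps. It says to study three more patients after 1/3, and it speaks of a total of six treated and evaluated. Its overrun example concerns patients 4 and 5, inside the cap. On that reading continued accrual only fills places 4 to 6, and the maxima stated elsewhere govern. This is a sensible reading and may be what was meant. However, no section says that accrual stops at six, Section 6.1.4 sets only a lower limit after 1/3, and the Appendix F sentence applies just as much while the sixth patient is under observation.

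The defence succeeds on size. The totals are exceeded only on an improbable path, and early window closure removes the excess.

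It also succeeds against several stronger inferences that a reader might draw:
- *That a fourth patient is unaccounted for.* After 0/3, Appendix F says what happens: a later DLT suspends the higher level until six are evaluated, and accrual there resumes only at no more than 1/6. The gap concerns a seventh patient after 1/6.
- *That the precision statements fail.* The confidence intervals in Sections 4.3, 6.1.3 and 9.4.3 rest on 13 patients at the RP2D, not on 28. Even with 28 enforced on the worst path, 7 + 7 = 14 are treated at that dose.
- *That the timeline proves a pause.* Eighteen patients at 5-6 weeks plus six 8-week pauses take 138-156 weeks, about 2.6-3.0 years, which matches Section 4.4. But that section gives an upper limit. Continuous accrual until the sixth level 3 patient (the 20th overall) is evaluated takes 20 x 5-6 + 8 = 108-128 weeks, about 2.1-2.5 years, which is also compatible.
- *That patients who are never infused add a known number.* The documents give no such rate, so the effect cannot be sized.

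**Conclusion.** The inconsistency holds; its numerical effect is modest and conditional. With evenly spaced accrual at the stated rate and full 56-day windows, Appendix F puts a seventh patient on any level that needs six evaluated. The worst case is 21 in escalation and 31 in total (30 if the extra level 3 patient is one of the ten), against 18 and 28. A reader might take 31 as the true maximum. The documents do not support that: Appendix F sets no limit, clustered arrivals could give more, and early closure gives 28.

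Two parts do not depend on these assumptions. Appendix F leaves a seventh patient after 1/6 without a counting rule, and it contradicts Section 9.4.2 on whether a higher level may open before everyone at the lower level has been observed. It is also unclear whether patients taken off protocol before infusion use up places in the cap.

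**What to change.** Reconcile the Synopsis, Sections 4.4, 6.1.3, 6.1.4 and 9.4.2 and Appendix F into one accrual rule. Two forms would each be consistent, and the choice is the sponsor's:
- State in Appendix F and Section 9.4.2 that accrual to a level stops at the stated cap until those patients are evaluated. The figures 6, 18 and 28 then hold.
- Keep continuous accrual, restate the maxima as conditional on pace and window length (7, 21 and 31 under the assumptions above), and say how an overrun patient's outcome enters the decision and whether one at the RP2D counts among the ten.

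Under either form, settle the difference between Section 9.4.2 and Appendix F on opening the next level, and say whether the cap counts enrolled or infused patients. Deleting only the quoted Appendix F sentence is not enough, because the text after it on additional patients would still conflict with Section 9.4.2. The cost is wording. The first form also fits the stated timeline; the second may need approval of a larger maximum.

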### 6.1.4 DEFINITION OF DOSE-LIMITING TOXICITY

Number of Patients with DLT at a Given Dose Level	Escalation Decision Rule	
0 out of 3	Enter 3 patients at the next dose level.	
≥ 2	Dose escalation will be stopped. This dose level will be declared the maximally administered dose <highest administered="" dose="">. Three (3 additional patients will be entered at the next lowest dose level if or 3 patients were treated previously at that dose.</highest>	
1 out of 3	
 
Enter at least 3 more patients at this dose level.
 
If 0 of these 3 patients experience DLT, proceed to the next dose level.
 
If 1 or more of this group experience DLT, then dose escalation is stopped, and this dose is declared the maximally administered dose. Three (3) additional patients will be entered at the next lowest dose level if only 3 patients were treated previously at that dose.
 
	
≤ 1 out of 6 at highest dose level below the maximally administered dose	This is generally the recommended phase II dose. At least 6 patients must be entered at the recommended phase II dose.	

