# 9.4.3 ANALYSIS OF THE SECONDARY ENDPOINT(S)

The RP2D is defined as the dose level selected to be evaluated in the expansion cohort or future phase II studies and will be equivalent to the MTD determined in the Phase 1b portion of the study. Once we determine the RP2D level, we will enroll 10 additional eligible patients and treat with the RP2D level. The goal for this expansion cohort is to evaluate the safety and tolerability for patients who will be treated with NE-DLI in the RP2D dose level, and to evaluate the preliminary efficacy estimate for the ORR. Including the dose escalation portion in which 3 or 6 enrolled patients will have been treated at the RP2D level, a total of at least 13 patients will be treated at the RP2D level. Based on previous data, (99) the complete response rate using microtransplantation was in the range of 36%-52% for MDS or AML from antecedent MDS patients. Hence, for the phase 2 portion, an ORR of 45% is considered clinically meaningful. With a sample size of 13 patients, if our ORR is 45%, the 95% CI (exact binomial) will be (18-74%); if the ORR is 50%, the 95% CI will be (22-78%). The response rates, including ORR and hematologic response by IWG 2006 criteria will be estimated via an exact binomial test with 95% confidence interval in combining patients treated at the RP2D dose level and the expansion cohort patients.

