#### 9.4.6 PLANNED INTERIM ANALYSES

See section 9.4.2. If the first dose level exceeds the MTD, the study will be suspended.

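### For 2 or more DLTs at dose level 2 or 3, Appendix F's accrual hold is not reconciled with the MTD and enrolment steps in sections 4.3, 6.1.3, 6.1.4 and 9.4

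*Combined protocol and SAP*

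**What the plan says.** Appendix F (12.6) closes with a trial-level rule: "If 2 or more of the first 6 patients on any dose level experience DLTs, accrual to the trial will be suspended". The IDE sponsor then opens a formal consultation with the FDA on whether the toxicities are attributable to the device, and "Subsequent accrual to the trial may resume only with permission from the FDA".

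The main text treats the same DLT count as follows.

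- Section 9.4.2, with matching text in 4.3 and 6.1.3: after 2 or more DLTs in a cohort of three or six, "the dosage level exceeds the MTD and the previous dose level will be declared as the MTD". A suspension is stated for the first dose level.
- Section 9.4.6 gives the whole planned interim rule as "See section 9.4.2. If the first dose level exceeds the MTD, the study will be suspended".
- The table in 6.1.4 says for 2 or more DLTs: "Dose escalation will be stopped". It then directs further enrolment. In the row for one DLT in three followed by another, the wording is "Three (3) additional patients will be entered at the next lowest dose level if only 3 patients were treated previously at that dose". The row for 2 or more carries the same instruction, though its text is partly damaged in the copy reviewed.
- Section 9.4.3, again matched in 4.3 and 6.1.3: "Once we determine the RP2D level, we will enroll 10 additional eligible patients and treat with the RP2D level".

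Appendix F's own decision list, earlier in the same appendix, prescribes for two DLTs in three patients only that escalation stops. Sections 4.1 and 9.4.1 cite Appendix F as the source of the 3+3 schema, so the appendix is operative text.

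**The concern.** One event, a failed level 2 or 3, leads to different statements about whether the next patient may be enrolled. Exceeding a level is an ordinary way for a 3+3 design to find its MTD, so the trial could well reach this point. Section 2.2.2 also reports a fatal cytokine release syndrome in the one earlier patient given the cell dose that is level 2 here. That patient had different conditioning and a related donor, so no DLT rate can be taken from it, but failure above level 1 is not a remote possibility.

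What is at stake is control of accrual after a safety signal. The section that defines the primary analysis and the section headed planned interim analyses both omit a hold that needs a regulator's permission to lift. Someone checking conduct against the plan could not tell whether enrolling the next patient followed the protocol or departed from it.

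**Working it through.** **Step 1: is the trigger the same?** Appendix F counts 2 or more DLTs in the first six patients at a level. Section 9.4.2 counts 2 or more in a cohort of three or among six. Under the 3+3 steps, a level that fails 9.4.2 also meets the Appendix F count.

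**Step 2: follow one case.** Take 0 of 3 DLTs at level 1, then 2 of 3 at level 2.

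| Text | What happens next | FDA condition stated? |
|---|---|---|
| 4.3, 6.1.3, 9.4.2 | Level 1 is the MTD; suspension stated for failure of level 1 | No |
| 9.4.6 | Refers to 9.4.2 and repeats the level 1 suspension | No |
| 6.1.4 table | Escalation stops; three more patients enter at level 1 | No |
| 4.3, 6.1.3, 9.4.3 | Once the RP2D is determined, 10 more patients are enrolled at it | No |
| Appendix F, decision list | Escalation stops | No |
| Appendix F, closing paragraph | Accrual to the trial is suspended | Yes |

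No section ranks these instructions or puts them in order. If the Appendix F hold applies at every level, the separate suspension for level 1 adds little, because Appendix F already covers that level.

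**Step 3: how often would the passages diverge?** The plan states no probability of suspension, so there is no figure to reproduce. It also gives no true DLT rates; those below are assumptions.

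For true DLT rate p, a level passes with 0 of 3 DLTs, or with 1 of 3 followed by 0 of 3:

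P(pass) = (1−p)³ + 3p(1−p)² × (1−p)³ = (1−p)³ + 3p(1−p)⁵

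| p | P(pass) |
|---|---|
| 5% | 0.8574 + 0.1161 = 0.9734 |
| 10% | 0.7290 + 0.1771 = 0.9061 |
| 20% | 0.5120 + 0.1966 = 0.7086 |
| 25% | 0.4219 + 0.1780 = 0.5999 |
| 30% | 0.3430 + 0.1513 = 0.4943 |
| 40% | 0.2160 + 0.0933 = 0.3093 |

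P(level 2 or 3 fails) = P(level 1 passes) × [1 − P(level 2 passes) × P(level 3 passes)]

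- 5/10/20%: 0.9734 × (1 − 0.9061 × 0.7086) = 0.348
- 10/20/30%: 0.9061 × (1 − 0.7086 × 0.4943) = 0.589
- 10/25/40%: 0.9061 × (1 − 0.5999 × 0.3093) = 0.738

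Level 1, where both texts suspend, fails with probability 1 − 0.9734 = 2.7% in the first scenario and 1 − 0.9061 = 9.4% in the other two. Across a wider set of assumed curves, the chance that level 2 or 3 fails runs from 16% (10/10/10%) to 83% (10/30/50%).

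**The case against.** The strongest reply is that both texts can be obeyed. Section 9.4.2 answers a dose question (which level is the MTD), and the closing paragraph of Appendix F answers an accrual question (pause, consult, resume). A team could declare the MTD, hold accrual, obtain permission and then enrol. Silence about a hold is not an instruction to ignore it, and 4.1 and 9.4.1 send the reader to Appendix F. This reading is possible and cannot be excluded. It is also not written down: the 6.1.4 table and 9.4.3 enrol without that condition, and the reading leaves little purpose for a suspension rule specific to level 1.

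Several stronger readings are tempting, and the documents do not support them.

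- A reader might infer that the main text limits suspension to level 1. Sections 9.4.2 and 9.4.6 name level 1 alone but do not say that no other suspension exists. Level 1 is also a special case, since no lower level can be declared the MTD. Section 10.1.2 adds a general power to suspend for unacceptable risk at any stage, with resumption once the sponsor, IRB and/or FDA are satisfied. That power is discretionary and does not name the 2-DLT trigger, so it does not settle the matter.
- A reader might infer that 9.4.2 and 9.4.6 themselves direct the trial into expansion. They do not; that step is in 4.3, 6.1.3 and 9.4.3.
- A reader might infer that Appendix F halts the whole study. It suspends accrual.
- A reader might infer that Appendix F governs the expansion cohort. Its title concerns dose escalation, and expansion has its own rules in 6.1.4 and 9.4.4. However, its wording covers any dose level, and 4.3 allows the RP2D to have only three escalation patients. The first six at that level could then include expansion patients. This is an ambiguity, not a demonstrated conflict.

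**Conclusion.** The point holds as an unreconciled instruction. After 2 or more DLTs at level 2 or 3, the protocol states an accrual hold that only FDA permission can lift. It also states MTD and enrolment steps that do not mention the hold, and gives no order between them. At level 1 both texts suspend, although only Appendix F states an FDA condition for resuming.

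The 35%, 59% and 74% figures size the chance of reaching the point where the passages diverge. They depend entirely on the assumed DLT curves. A reader might take them as the chance that patients would be enrolled in breach of a hold. They are not: that depends on which text the team follows, and it would be zero if the team applied the hold first.

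This should be corrected, because it bears on whether patients may be enrolled after a safety signal. No view is taken on which rule is right.

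**What to change.** Reconcile 4.3, 6.1.3, the 6.1.4 table, 9.4.2, 9.4.3, 9.4.6 and both parts of Appendix F (the decision list and the closing paragraph) so that they:

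- state one trial-level action for 2 or more DLTs at each dose level;
- give the order of that action relative to declaring the MTD, entering further patients one level down, and opening expansion;
- say whether the Appendix F sentence covers expansion patients at the RP2D, alongside the expansion rules in 6.1.4 and 9.4.4;
- cross-reference any accrual hold in 9.4.2, 9.4.6 and the 6.1.4 table.

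The content of the rule is for the sponsor to decide. The cost is protocol wording only, with no added patients or procedures.
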